The village nutrition management committee will be met at the onset of the study to discuss the objectives of the study, the level and types of input and cooperation that can be mobilized will be planned. A local volunteer will be identified to work for the project selected by the village nutrition committee. Village women's group will meet to plan their time and availability for demonstration and advocacy of measures undertaken for the research projects. The proportion of activity that can be channeled through the CNP and time available for the CNP will be determined. Normally nourished 6-9 month old infants, mild and moderately malnourished children less than 2 years will be taken from the CNP registrar and GMP cards. The proportion of moderately malnourished children with growth faltering and who are receiving supplementary feeding will be excluded from the study. It is known that in health intervention, there is visit effect, where regular visits of health workers indirectly influence caregivers to ask about child's well being and seek advice. To minimize the effect all groups will receive same number of visits for information collection.

Design of the project:

This will be a prospective longitudinal intervention study. The study will have

- a) a management approach and
- b) a preventive approach.

Management approach study groups

- (1) One intervention group of moderately malnourished children without growth faltering will

receive **intensive nutrition education** (INE) and demonstration of appropriate complementary feeding at home in same intensity of recently completed study at Shahrasti thana in Chandpur district. The education will include food demonstration, specific education on diet, components of caring practices, and disease control linking to the referral system.

- (2) The second intervention group will be moderately malnourished children without growth faltering who will receive **less intensive nutrition education** (LINE) food demonstration and specific education on diet, components of caring practices, and disease control linking to the referral system.

Preventive approach study groups

- (3) The third group will be the preventive group with mildly malnourished children and well-nourished 6-9 months aged infants who will receive less intensive nutrition education same as the second group of moderately malnourished children

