(c) Another preventive group of well-nourished 6-9 month aged infants for complementary feeding will be randomized by CNCs into either to less intensive nutrition education or no nutrition education.

Staff training:

A staff-training curriculum will be developed on the basis of the experience of the recently completed operations research at Shahrasti. A module of training manual will also be produced to fulfill the adaptation need of the CNP/CNO's with newer findings of the project. Staff training will be at Dhaka. Another training manual will be prepared for mothers according to earlier study and FGD reports.

Quantitative data collection

One health assistant (preferably graduate level having recognized ability to communicate with village mothers) will be appointed to provide nutrition education and collection of data in the area covered by 3 CNCs. There will be one supervisor with nutrition background to train the health assistants and organize and supervise nutrition education on child feeding and caring practices. Investigators will train and guide the health assistants. An anthropologist and a nutritionist will participate in counseling on child feeding and caring practices.

Anthropometric data will be collected monthly from the GMP sessions with accuracy ensured. Accuracy of weighing scales will be tested against a known weight by health assistants. The project nutritionist will also standardize the weighing method. Separate study data will be collected if the quality of anthropometry of CNPs is not acceptable. A project physician will record a base line clinical assessment of deficiency signs of micronutrients. Weight will be taken using salter scale (UK) (sensitivity 100g). Length will be measured by a locally constructed length board with precision of 1mm. Staff will be trained by Investigators and nutritionist. MUAC- data will be collected with TALC (Teaching Added at Low Cost)(UK) tape with causes of 2 mm.

Data on compliance level of nutrition education will be collected during 2 weekly observation period. Data on causes of noncompliance will be also recorded. Changes in child feeding frequency and changes in dietary composition will be recorded

Referral system and disease control

A project medical officer will educate on timely referral to Thana Health Complex (THC) or FWC during illness of the child. A communication with THC medical officer will be strengthened for BINP initiatives for malnourished children.

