Collection of morbidity data:

Morbidity information will be collected at two weekly home visits during study period using pre-tested questionnaire.

Operational definition

Fever: If the temperature is more than normal, that is above 38.5⁰ C is called fever.

In the field level:

1. When mother tell about her child suffered from fever that lasted for 1 day, a physician will examine the child and child will be treated at home for mild fever.
2. When mother will tell that her child has fever lasting for two to three days, it will be regarded it as moderate fever.
3. Mother will tell that fever lasts for more than three days, he will be examined and regarded as sever fever.

Diarrhoea: An episode of diarrhea is defined as the passage of three or more loose or watery stools within 24 hours. Records will be collected on consistency and the number of stools per day.

1. A child passing loose, liquid or watery stool more than three times per day will be called acute diarrhoea.
2. Presence of blood with stool will be define as invasive diarrhea.
3. When a single episode of diarrhea lasts for more than two weeks, it will be called persistent diarrhoea.

Ear Infection: A child will have pain in ear, fever, with watery or purulent secretion from one or both ear will be diagnosed as ear infection.

Lower respiratory tract infection: When a child suffering from cough and fast breathing more than 50 per minute, fever, or chest indrawing will be defined to have lower respiratory tract infection (LTRI).

Upper respiratory tract infection: A child suffering from cough and cold without sings of LRTI will be diagnosed as upper respiratory tract infection (URTI).

Skin infection: A child suffering from skin disease with impetigo or skin infection or scabies will be define have skin infection.

Sore on Tongue: Ulceration or fissure on tongue or palate will be identified as sore tongue.

Angular stomatitis: Any child having signs of ulceration or excoriation in angle of mouth will be diagnosed to have angular stomatitis.

Xerpthalmia : Conjuntival haziness & corneal haziness will be diagnosed as Xerophthalmia.

The subjects will be referred to THC by interviewers during two weekly home visits if following conditions develop:

Referral will be done accordingly to IMCI criteria in the following ways:

1. Pneumonia: After 2 days of first time of antibiotic therapy:

Check the child for general danger signs.

Assess the child for cough or difficult breathing.

Ask:

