FGD will be conducted on mothers in 6 groups each from 3 CNC's (1 control and 2 study areas). There will be 6-8 mothers of moderately malnourished children in each Focus Group Discussion. This is expected to be more or less homogenous, since mothers having young children in the villages are of similar age FGD will be conducted by the anthropologist. Moderator will play the role of guiding the group on the right topic by putting them on the track. The research personnel will facilitate discussion but they will not influence the discussion. A tape recorder will be used to record the discussion. One facilitator will take notes. Obtained data from FGD will be analyzed manually by using coding.

The FGD will be conducted again to evaluate the change in behaviour and the process indicators. The method indicated above will be followed in the later part of the study.

A pre-test on knowledge of child feeding practice will be done and will be repeated with same the questionnaire after the diet counselling sessions with the mothers. Data on feeding frequency, preparation of information on child feed, dietary ingredients, frequency of feeding and constraints will be recorded at two weekly intervals in study groups. Post test will be conducted at the end of

nutrition education period.

The health assistants will be pre-testing the nutrition knowledge of the mothers and mothers will be observed before actual training is given. These subjects will not be included into study. This will reduce observer bias of the health assistants.

Outcome variables:

1. Mothers understanding and ability to identify moderate malnutrition in children.
2. Mothers understanding on consequence of moderate malnutrition.
3. Change in knowledge of mothers in feeding practices.
4. Frequency of home feeding (Breast-feeding and supplementary feeding).
5. Frequency of seeking medical care during illness, referral, incidence, duration of illness.
6. Adequacy of child feeding, frequency & type of feeding.
7. Weight gain, weight for age and weight for height at the end of intervention.
8. Proportion of complementary feeds in 6-9 months age group.
9. Nutritional status of children at various phases of intervention and observation.
10. Adaptation level of nutrition education program by CNP, CNO.
11. Constant of not practicing education knowledge.

Secondary outcome variables: -

1. Incidence and prevalence of diarrhoea and ALRI
2. Referral success and failure
3. Resistance to education

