Data will be double entered in a microcomputer within a week of data collection. The field supervisors will visually check data before sending for entry into the computer. Any error, discrepancy or omission found during data entry will be reported to the investigators without delay. Data will be entered into microcomputer using SPSS Windows's program. Data on weight gain, frequency and introduction of complementary feeding will be compared between experimental groups. Complementary feed introduction and regularity will be compared among 6-9 month age groups in education and control groups. Comparability between intervention and control groups will be assessed by baseline characteristics such as age sex, nutritional status, socioeconomic characters, feeding practices, etc. Continuous variables will be assessed for normal distribution. T test will be performed to compare data of normal distribution; otherwise non-parametric test will be used. Chi-squared test will be performed for categorical variables, Multiple regression analysis will be done with weight gain as dependent variable and intervention and potential confounding variables such as age, sex, SES, baseline nutritional status, infection as independent variables. Separate analysis will be performed for periods of intervention, reinforcement and observation.

Compliance of nutrition education will be measured at 2 weekly observation period (already mentioned). Compliance will be measured as process indicator. Comparison of compliance will only

be done at the end of the study so that the investigators will have no idea about which group is more a less compliant. Therefore, these will be little change of introduction of bias due to non-compliance, effect of intensive or less intensive nutrition education will be compared as a whole. So complain will be seen as a factor of nutrition education with given intensive. Analysis of compliance data will be done by relating to the outcome effect of nutritional status and can be compared between two education groups.

Analysis of qualitative data

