12. Only iodized salt should be used in the household food preparation. Adequate dietary iodine improves growth and increases intelligence and its absence cause growth failure, failure in life skills.

About egg:

13. Each egg contains a high proportion of essential amino acids necessary for growth, is rich in fat and contains very good quantities of calcium, iron, zinc, vitamin A and D and also thiamin and riboflavin.

About fat:

14. Fat is important because it has more than twice (9 Vs 4 kcal per gram) as much energy as carbohydrates, or protein. Thus it can reduce the bulk of the diet. Child need more energy in small amount of diet as his stomach is small. It issues vitamin in body and adds good taste to diet.

About caring practice:

15. Caring practice would include washing and bathing as required. It included encouragement to the child to play and have attentions as soon as child demands. Other members of the family should give attention to child if he demands anything.

About personal hygiene:

16. Cleaning and identifying a feeding plate for the child would be necessary, as quantity of food will be known when a child has been give food in a defined container. A child needs adequate food for growth satisfactory.

Disease Control:

17. Mothers would be given counseling on disease control, such as advice on immunization at time, referral to health family in illness. Preventive care for cold, and taking to FWCs for ARI, high fever, and diarrhoea frequent is necessary.
18. Counseling will be done how to identify moderate degree malnutrition. GMP card available in family or CNC will used. Counseling will be given on consequence and risk of malnutrition from disease or inadequate feeding of a child.
19. Village Nutrition Management Committee (VNMC) will be given regular orientation during monthly meetings to accept the philosophy that children of their own village should be healthy and they can remove child malnutrition from their village if they follow and guide a few simple principles about child care and feeding.

Annexure 2

ABSTRACT SUMMARY FOR ETHICAL REVIEW COMMITTEE

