Weight gain was correlated negatively with age of the child, and body weight but positively height. Weight gain was negatively associated with prevalence of diarrhoea and febrile episode, blood in stool when controlled for other factors. There was no significant difference in net weight gain between the education and supplemented groups ($p < 0.1$). There was change in behaviour related to home feed preparation and identifying specific foods for child feeding in groups reducing nutrition education. There was a seasonal effect on disease pattern. At certain times, most of the children had suffered from fever and diarrhoea, which was followed by faltering body weight. Incidence of diarrhoea was 13/100-child month, 19/100-child month and 16/100-child month in control; education and supplementary feeding group respectively. Incidence of acute respiratory tract infection (ARI) was 10/100 child month, 3/100 child month and 2/100 child month during intervention in control, education and supplementary feeding group respectively. It was found that mothers did not have special idea on the quality and quantity issue of a complementary food for the child or recognizing a special need during rapid growth. Their practice of child feeding in time or frequency was traditional. Some mothers had idea that disease of a child is a God's will and they would take him to a local hekim for purified water or kabiraji treatment. Some mothers had strong belief that expensive foods or fruits like grapes, apples etc. form blood. They had believes on hot and cold food and practice of with holding food during illness was common. Food items such as oil and egg were considered to be too strong, gas producing and indigestible for young children. There were complaints of not getting attention in Thana Health Complex when they visited for treatment of their children.

Follow up FGDs at the end of three months intervention were conducted and showed significant important in negative ideas on adding oil to children's feed and addition of eggs in home made complementary feed cooked "Khichuri". Referral to medical service centres remained a problem of not getting service from the thana health centres during that need.

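### The adjusted weight-gain regression treats infection during follow-up as a confounder, so that one estimate does not give the total effect of the education package

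*Protocol*

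**What the plan says.** The model is set out in the Protocol, Data Analysis: "Multiple regression analysis will be done with weight gain as dependent variable and intervention", followed by "potential confounding variables such as age, sex, SES, baseline nutritional status, infection as independent variables". The word baseline is attached to nutritional status only.

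Other sections bear on what infection means here:

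- **Timing.** Under Collection of morbidity data: "Morbidity information will be collected at two weekly home visits during study period using pre-tested questionnaire". The baseline examination under Quantitative data collection has another purpose: "A project physician will record a base line clinical assessment of deficiency signs of micronutrients".
- **Content of the intervention.** Under Management approach study groups, both education arms are taught "components of caring practices, and disease control linking to the referral system". Annexure 1, Disease Control, adds: "Mothers would be given counseling on disease control, such as advice on immunization at time".
- **Status as an outcome.** Item 5 under Outcome variables reads "Frequency of seeking medical care during illness, referral, incidence, duration of illness". The first secondary outcome is the incidence and prevalence of diarrhoea and lower respiratory infection.
- **Earlier data.** Annexure 4, on the Shahrasti study: "Incidence of acute respiratory tract infection (ARI) was 10/100 child month, 3/100 child month and 2/100 child month during intervention", for control, education, and education plus supplementary feeding respectively.

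**The concern.** A confounder must precede the exposure, or at least not result from it. Allocation is random by CNC, so illness recorded afterwards cannot confound the comparison of arms. It can lie on the path from education to weight gain, because the education tries to prevent illness and get it treated.

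Conditioning on such a variable does two things. It removes whatever part of the effect runs through illness. If something unmeasured drives both illness and growth, it also makes the arms non-comparable within levels of illness. The objectives ask how well the whole package works, which is a total effect; the adjusted coefficient answers a different question. The protocol names no other covariate-adjusted estimate of the intervention effect, so readers may lean on this one if the CNCs differ at baseline.

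**Working it through.** **Step 1: is infection a baseline variable?** The morbidity questionnaire runs during follow-up. The baseline physician assessment covers micronutrient signs. The baseline comparability list in Data Analysis does not name infection. The protocol describes no infection measure taken before allocation.

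**Step 2: does the intervention differ by arm in a way that could change infection?** From the table of session frequency and intensity in the Training plan, for referral and disease control:

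- Intensive arm (INE): 12 + 3 = 15 sessions.
- Less intensive arm (LINE): 6 + 3 = 9 sessions.
- No-education controls: none, from the description of the fourth study group.

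**Step 3: is infection related to weight gain?** Annexure 4 reports that weight gain was negatively associated with diarrhoea, febrile episodes and blood in stool. ARI is not named there.

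**Step 4: how large could the shift be?** The protocol states no figure for this, so there is none to reproduce. Inputs from Annexure 4, education against control (standard BINP advice):

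- Three-month weight gain 910 g against 636 g: difference 910 - 636 = 274 g.
- ARI 3 against 10 per 100 child-months.
- Diarrhoea 19 against 13 per 100 child-months.

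Two assumptions are needed. The diarrhoea rates are applied to the same three months as the ARI rates. Each episode costs 100-300 g, a range the documents do not give.

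Formula: shift = difference in episodes per child × grams per episode.

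- ARI: (10 - 3)/100 × 3 = 0.21 fewer episodes with education.
- Diarrhoea: (19 - 13)/100 × 3 = 0.18 more episodes with education.
- Net: 0.21 - 0.18 = 0.03 fewer episodes.

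| Infection entered as | Shift at 100 g | Shift at 300 g | Adjusted difference | Share of 274 g |
|---|---|---|---|---|
| ARI only | -21 g | -63 g | 253 to 211 g | 8% to 23% |
| Diarrhoea only | +18 g | +54 g | 292 to 328 g | 7% to 20% |
| Both | -3 g | -9 g | 271 to 265 g | 1% to 3% |

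**Step 5: what if there is an unmeasured common cause?** A large simulation (2,000,000 children) used the ARI rates, 100 g per episode and a true direct effect of 253 g.

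- With no common cause, the model without infection gave about 274 g and the model with infection about 253 g.
- An assumed frailty was then added that raised infection and lowered weight gain by 100 g per standard deviation. The model without infection gave about 273 g and the model with infection about 242 g.

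The second adjusted value is neither the total effect nor the direct effect. This shows the mechanism only; the frailty is invented for the purpose.

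**The case against.** **The regression does not decide the trial.** The management sample size rests on the proportion improving from moderate malnutrition. The t-tests, non-parametric tests and chi-squared tests are not adjusted for infection, so an unadjusted weight-gain comparison is already planned. This stands. A reader might infer that the trial's effect estimate as a whole is biased; the documents do not support that, because only the adjusted weight-gain coefficient is touched.

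**The model could be explanatory.** Annexure 4 relates weight gain to illness with other factors controlled, and the response to external comments speaks of considering the determinants of growth together. Infection would be legitimate in such a model. But Data Analysis puts it beside the intervention term under the label of confounder and does not say that the coefficient is to be read as anything but the intervention effect.

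**The arms may hardly differ in infection.** The Project Summary promises equal referral advice to all groups, and the response to external comments disclaims extra morbidity control. Both education arms are taught disease control, so the INE-LINE shift may be smaller than the earlier study suggests. That is fair as to size. These statements still do not turn infection into a baseline variable, and they sit awkwardly with the 15, 9 and zero disease-control sessions.

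**The earlier rates are weak evidence of cause.** Annexure 4 gives no test for the infection rates, notes a seasonal pattern in disease, and had five CNCs per group. A reader might infer that education reduced ARI and that adjustment would therefore shrink the effect by 8% to 23%. That figure uses ARI alone, while the covariate is infection in general and diarrhoea went the other way.

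**Infection is not explicitly dated in the model.** True. Follow-up infection is an inference, though the only one the described data allow.

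**Conclusion.** The point holds for the covariate-adjusted weight-gain regression only. As written, its intervention coefficient is not the total effect of the education, because it conditions on a variable recorded after allocation that the education targets and the plan itself counts as an outcome. Further bias is possible but depends on unmeasured common causes that the documents do not establish.

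Size and direction cannot be fixed in advance. They depend on how the undefined term infection is coded, on a weight loss per episode that the documents do not give, and on rates from a comparison of education with standard BINP advice. The documents offer no corresponding figure for INE against LINE, or for LINE against no education. If both illnesses are entered at equal cost per episode, the net shift may be close to nil. The case for change rests on what the coefficient means, not on a demonstrated large distortion.

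**What to change.** Remove infection from the model that estimates the intervention effect, and keep age, sex, socioeconomic status and baseline nutritional status. If adjustment for illness is wanted there, use only infection status measured before allocation. Report infection by arm as the outcome it already is. If its role in weight gain is of interest, fit a second model that includes it, label that model exploratory or mediation, and do not present its arm coefficient as the treatment effect.

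The main change costs one covariate and a sentence in the analysis section, with no change to data collection or sample size. Only the option of a pre-allocation infection measure would need something added: a morbidity question at enrolment.
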